### 3.12 Analysis Schedule

Analyses will be performed as per the Communication Plan, after 335 and all patients have completed the study.

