#### **Patient Discontinuation from the Study:**

Patients could be withdrawn from the study at any time by the treating physician or on their own accord. Patients that participate in another trial will be withdrawn from the study. Patients that terminate treatment or switch from their current treatment will be followed for the 24 month study follow up period. Patients may change treatment at the discretion of the physician including switching from one of the defined treatment cohorts to another. Lack of therapeutic response, low compliance to treatment or the incidence of adverse events will not necessitate study withdrawal.

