#### 10.3 Sample Size Calculations

Sample size considerations are based on the primary objectives of the study, specifically the proportion of patients that achieve a PGA rating of "0" or "1" at 24 months of follow up.

The following data and assumptions were used to determine the sample size requirements for the study:

- In the Champion study after 16 weeks of treatment 73% of the patients treated with adalimumab, 30% of the patients treated with methotrexate and 11.3% of the patients treated with placebo achieved PGA values of 0 or 1 indicating clear or minimal disease.
- The Champion study was a randomized placebo controlled clinical trial that was based on a strict protocol not allowing any concomitant treatment and enrolling a very well defined patient population. In the current study we can assume that we will observe similar trends in the order of treatment effectiveness, by which adalimumab will be superior to traditional systemic agents, which will be superior to topical agents. However, due to case mix and use of concomitant medications the actual therapeutic effect and difference between groups may be more variable and lower than that observed in the CHAMPION study. We can therefore assume that due to patient profile, and in order to be conservative, that the observed proportion of patient achieving and maintaining a PGA≤ 1 at 6 months will be approximately 50%. A relative reduction of 20% (RR = 0.80) in PGA would be considered as the minimum acceptable for clinical importance. Therefore, the current study we should be powered to detect a 20% relative reduction between adalimumab and traditional systemic agents, and a similar difference between systemic and topical agents. It follows that if we assume that the proportion of patients treated with adalimumab that achieve PGA ≤1.0 at six months will be

50%, the proportion in the patients treated with traditional systemic agents will be 40% ( $\underline{RR}$ =0.8) and that in patients treated with topical agents will be 32% ( $\underline{RR}$  = 0.8).

• For an expected treatment group ratio of 1:1 for adalimumab: traditional systemic agents and topical agents a total of 360 (180: 180) patients will be required for 80% power and two tailed significance of 5%. Assuming a 25% attrition rate and allowing for 100 additional patients (10 per variable) in the multivariate analysis 660 (330:165:165) patients will be recruited.

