## 2.7 Sample Size

Assuming a 25% attrition rate and allowing for 100 additional patients (10 per variable) in the multivariate analysis, for a treatment group ratio of 2:1:1 for adalimumab, traditional systemic agents and topical agents a total of 660 (330:165:165) patients will be required for 80% power and two tailed 5% significance. In addition, this sample size will be sufficient to detect a 20% (Relative Risk = 0.80) relative reduction in PGA between adalimumab and traditional systemic agents, and a similar difference between systemic and topical agents.

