## 3 Statistical Methods

## 3.1 Statistical Handling Policy

### 3.1.1 Analysis Conventions

This section details general guidelines to be used for the statistical analyses. Deviations from these general policies may be given in the specific detailed sections of this statistical analysis plan. When this situation occurs, the rules set forth in the specific section take precedence over the general conventions. The following policies will be applied to all data presentations and analyses:

- Two-tailed tests will be performed for all analyses that use statistical testing with a significance level of  $\alpha = 0.05$ .
- All p-values will be rounded to 3 decimal places. All p-values that round to 0.000 will be presented as '<0.001' and p-values that round to 1.000 will be presented as '>0.999'. Any p-value  $\leq$ 0.05 will be considered statistically significant.
- Summary statistics will consist of the number and percentage of responses in each category for discrete variables, and the mean, median, standard deviation (SD), minimum, maximum, and 95% confidence interval for continuous variables.

COMPLETE - PS Statistical Analysis Plan Version 3.0 July 23rd, 2015 Page 24 of 231

- All mean and median values will be formatted to one decimal place. Standard deviation values will be formatted to two decimal places.
- All percentages will be rounded to one decimal place. Where appropriate, the number and percentage of responses will be presented in the form XX (XX.X %), where the percentage is in the parentheses.
- All listings will be sorted for presentation in order of treatment group, site number, subject number, and date of procedure or event.
- When necessary for analysis purposes, partial dates will be completed (i.e., turned into complete dates) using the most conservative approach. Where appropriate, all analysis and summary tables will have the population sample size for each treatment group in the column heading.
- All analyses and summary tables will have the population sample size for each treatment group in the column heading.
- Tables will include footnotes describing the analyses involved, and listings of covariates included in the analyses, where relevant.

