## 3.11 Analysis of the Secondary Objectives

Between groups differences with respect to the changes in the BSA, PGA, DLQI, PASQ, BDI, SF-36 WLQ from baseline to 24 months of treatment will be assessed with One Way ANOVA or repeated measures, mixed effects general linear model adjusting for potential confounders or the propensity score. Planned contrasts will be used to assess between group differences at the other follow up time points. Pairwise between group comparisons will be adjusted for multiplicity with the Tukey's Least Significance Test.

In order to better assess the impact of the treatment received and changes in the regimen the treatment will be handled as a time-dependent covariate in these analyses. Descriptive statistics will be used to assess the between-group differences in healthcare resource utilization and healthcare costs associated with PS. With respect to achieving therapeutic response end points and incidence of articular and extra-articular manifestations between group differences will be assessed with multivariate logistic regression while Cox proportional hazard models will be used to assess between group differences with respect to the time of achieving therapeutic response and first occurrence of articular and extra-articular manifestations.

Descriptive statistics will be used to assess the regional differences with respect to baseline patient characteristics and disease parameters. Descriptive statistics will also be used to assess the practice patterns of Canadian dermatologists in the management of patients with

### COMPLETE - PS Statistical Analysis Plan Version 3.0 July 23rd, 2015 Page 31 of 231

moderate to severe Plaque PS. The study cohort will be divided into Canadian regions as Quebec, Ontario, Maritimes and Western Canada.

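### SAP 3.12 plans analyses after 335 and after all patients under the same p ≤ 0.05 rule, without saying which is confirmatory or which patients the first includes

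*SAP*

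**What the plan says.** The timing is set in SAP 3.12, which is a single sentence: "Analyses will be performed as per the Communication Plan, after 335 and all patients have completed the study". The Communication Plan is not among the documents.

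The decision rule is in SAP 3.1.1. It opens with "The following policies will be applied to all data presentations and analyses", then states "Two-tailed tests will be performed for all analyses that use statistical testing with a significance level of" 0.05, and adds that any p-value at or below "0.05 will be considered statistically significant". A specific section may override these conventions, but SAP 3.12 does not.

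The only multiplicity provision is in SAP 3.11, for the secondary outcomes: "Pairwise between group comparisons will be adjusted for multiplicity with the Tukey's Least Significance Test". It concerns group comparisons, not repeated analyses.

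SAP 3.5 bases effectiveness analyses on an ITT population defined by consent, eligibility and at least one dose. Completing the study is not a condition. SAP 2.7 gives the planned size: "a total of 660 (330:165:165) patients will be required for 80% power and two tailed 5% significance", after an allowance for 25% attrition.

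**The concern.** Two analyses under one significance rule give two chances to declare a difference. No stopping rule is needed for this to matter; it is enough that a result at or below 0.05 may be claimed at either time. As written, the SAP allows that, because it does not reserve the confirmatory claim for the final analysis.

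The second question is who is in the first analysis. The primary endpoint is at month 6 (Protocol 5.3.1, SAP 2.10.1.1 and 3.10), whereas the trigger is completion of a 24-month study. If the data set were limited to the patients who met the trigger, month-6 response would be estimated in patients selected on a later event.

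SAP 3.2 also leaves the method of confounder adjustment open until the data are seen. Outcome results from a first analysis could be known before that choice is settled. This adds risk, but it cannot be quantified from the documents.

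**Working it through.** The documents state no overall error rate for the two analyses. The only figure to reproduce is the nominal 5% for a single test, which the formula below returns as t approaches 1.

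**Inputs**
- First analysis: 335 patients (SAP 3.12).
- Planned total: 660 (SAP 2.7; Protocol 10.3).
- Attrition: 25% (same sections), so 660 × 0.75 = 495 expected to remain.
- Level: two-sided 0.05 at each analysis, critical value 1.96 (SAP 3.1.1).
- Recruitment over 24 months (Protocol 6.2); follow-up 24 months (Protocol 6.4); primary endpoint at month 6.
- Assumption, not in the documents: patients enrol at a uniform rate.

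**Error rate for one contrast**

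Let t be the share of the final primary-endpoint information available at the first analysis. Under no difference, the two test statistics are approximately bivariate normal with correlation √t, and

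overall error = 1 − P(|Z1| < 1.96 and |Z2| < 1.96).

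| First data set | t | Overall two-sided error |
|---|---|---|
| Only the 335, of 660 | 335/660 = 0.508 | 8.3% |
| Only the 335, of 495 | 335/495 = 0.677 | 7.7% |
| Illustrative | 0.90 | 6.5% |
| Illustrative | 0.99 | 5.5% |
| All month-6 data | approaching 1 | 5.0% |

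Two independent tests would give 1 − 0.95² = 9.75%, an upper bound.

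**How much month-6 data exist at the first cut**
- The 335th of 660 patients enrols at 335/660 × 24 = 12.2 months and reaches month 24 at 12.2 + 24 = 36.2 study months.
- If 335 counts only patients who stay to the end, about 335/0.75 = 447 must have enrolled. The 447th enrols at 447/660 × 24 = 16.3 months, so the trigger falls at about 40.3 study months.
- The last patient enrols at month 24 and reaches month 6 at 24 + 6 = 30 study months.

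On either count, every month-6 window has passed before the first analysis. If all available month-6 data are used, t is close to 1 and the inflation is close to nil. If only the 335 are used, the figure is 8.3% or 7.7%.

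**Who is in the first data set**

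The passages point in different directions:
- SAP 3.12 says when the analyses run. It does not state a population.
- SAP 3.5 fixes an ITT population without a completion requirement.
- SAP 3.12 also speaks of all patients having completed, while 25% attrition is assumed. There, completion may mean only that participation has ended.
- Protocol 9.0 records final status as either completed or withdrawn, and SAP 3.6 separates completers from discontinuations. There, completion excludes those who withdrew.

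The word is ambiguous, and SAP 3.12 does not resolve it.

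**The case against.** The strongest reply is that there is no stopping rule and no design change, so the final test taken alone keeps its 5% level. That is correct. The inflation belongs to a claim allowed at either time, and it disappears once the final analysis is named as the only confirmatory one. The SAP does not name it. The unseen Communication Plan may do so, but Protocol 10.1 assigns the detailed description of the analyses to the SAP.

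Three stronger readings are tempting, and the documents do not support them.

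- A reader might infer that the first data set is selected on completing 24 months. The sentence can equally be a data-cut trigger, and SAP 3.5 points to ITT. Leaving treatment is also not leaving the study: under Protocol 6.5.1, "Patients that terminate treatment or switch from their current treatment will be followed for the 24 month study follow up period". Any figure for the resulting bias would need response rates in early leavers, which the documents do not give.
- A reader might infer that the 5% level simply fails for the primary endpoint. That depends on the data set; with all month-6 data at the first cut it is nearly kept.
- A reader might combine the two analyses with the treatment contrasts and quote 15.4% (two adalimumab contrasts) or 19.3% (all three). A single analysis with unadjusted contrasts already gives 9.4% or 12.1%. That part is a separate issue and should not be attributed to SAP 3.12.

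**Conclusion.** The point holds in a limited form. Two analysis times share one significance rule, and the SAP does not say which is confirmatory. For a claim allowed at either time, the false-positive rate per contrast on the month-6 primary endpoint is about 5% to 8.3%. The range reflects an unstated choice of data set. Its upper end assumes that only the 335 patients are analysed first; its lower end assumes that all month-6 data are used and accrual is uniform over 24 months. The lower end would not apply if recruitment overran, or if more than half the sample enrolled in the first six months.

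Restriction to completers is an ambiguity to resolve, not a stated feature of the plan. If it were intended, it would conflict with SAP 3.5 and expose the early results to attrition bias of unknown size.

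**What to change.** In SAP 3.12, state that:

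1. The 335-patient analysis is descriptive: estimates and confidence intervals, with no significance claim and no reading of an interval as a test.
2. The final analysis is the only confirmatory test, at two-sided 0.05.
3. Reaching 335 completions is only the trigger for the data cut. The first analysis uses all ITT patients with data at the cut-off, whether or not they completed the study.

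This changes SAP wording only. Recruitment, visits, sample size and the final significance level stay as they are. The downside is that the early analysis yields no formal significance claim.

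If the sponsor wants such a claim, an alpha split is possible, but the data set must be settled first. For example, testing first at 0.001 leaves 0.0498 for the final analysis at t = 0.508. That split was computed for about half the information and should not be carried over to a first cut that already holds nearly all the month-6 data.
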